## Figures

Figure No.	Title	Population
4.1 Efficacy		
4.1.1	Kaplan-Meier Estimates of Progression-Free Survival	Phase 2 FAS Population
4.1.2	Kaplan-Meier Estimates of Overall Survival	Phase 2 FAS Population
4.1.3.1	Swim Plot of Duration of Response - by Treatment Group	Phase 1 FAS Population
4.1.3.2	Swim Plot of Duration of Response - by Treatment Group and Tumor Type	Phase 2 FAS Population
4.1.4.1	Waterfall Plot of Percentage Change From Baseline in Sum of Target Lesions - by Treatment Group and Dose	Phase 1 FAS Population
4.1.4.2	Waterfall Plot of Percentage Change From Baseline in Sum of Target Lesions - by Treatment Group and Tumor Type	Phase 2 FAS Population
4.1.5.1	Spider Plot of Percentage Change From Baseline in Sum of Target Lesions - by Treatment Group	Phase 1 FAS Population
4.1.5.2	Spider Plot of Percentage Change From Baseline in Sum of Target Lesions - by Treatment Group and Tumor Type	Phase 2 FAS Population
4.90 Safety Data		
4.90.1.1	Bar Chart for Incidence of Treatment Emergent Adverse Events of Special Interest - by Treatment Group and Dose	Phase 1 FAS Population
4.90.1.2	Bar Chart for Incidence of Treatment Emergent Adverse Events of Special Interest - by Treatment Group and Tumor Type	Phase 2 FAS Population
4.90.2.1	Line Graph of Selected Laboratory Values by Study Visit	Phase 1 FAS Population
4.90.2.2	Line Graph of Selected Laboratory Values by Study Visit	Phase 2 FAS Population
4.90.3.1	Box-and-Whisker Plot of Selected Laboratory Values by Study Visit	Phase 1 FAS Population
4.90.3.1	Box-and-Whisker Plot of Selected Laboratory Values by Study Visit	Phase 2 FAS Population

## Listings

Listing No.	Title
2.1 Discontinued Subjects (Subject Disposition)	
2.1.1	Subject Enrollment and Disposition Status
2.1.2	Subject Inclusion and Exclusion Criteria Violations
2.2 Protocol Deviation	
2.2.1	Protocol Deviations and Violations
2.3 Data Excluded From [REDACTED] Efficacy, and/or Safety Analyses	
2.3.1	Analysis Population
2.4 Demography and Baseline (Including Prior and Concomitant Medications)	
2.4.1	Demographic
2.4.2.1	Baseline Disease Characteristics for Phase 1 Solid Tumor Types
2.4.2.2	Baseline Disease Characteristics for Phase 2 – by Tumor Type

Listing No.	Title
2.4.3	Disease History
2.4.4	Prior Radiation Treatment
2.4.5	Prior Systemic Therapy
2.4.6	Prior Surgery or Surgical Procedure
2.4.7	Medical History
2.4.8	Prior and Concomitant Medication
2.5 Efficacy	
2.5.1.1	Best Overall Response With Confirmed CRs and PRs Under RECIST v1.1
2.5.1.2	Best Overall Response With Unconfirmed CRs and PRs Under RECIST v1.1
2.5.2.1	Best Overall Response With Confirmed CRs and PRs Under mRECIST v1.1
2.5.2.2	Best Overall Response With Unconfirmed CRs and PRs Under mRECIST v1.1
2.5.3	Overall Response Assessment
2.5.4	Response Assessment: Target Lesions
2.5.5	Response Assessment: Non-Target Lesions
2.5.6	Response Assessment: New Lesions
2.5.7	ECOG status
2.6 Adverse Events (and Exposure)	
2.6.1.1	Study Drug Administration for INCAGN01876
2.6.1.2	Study Treatment Administration for Nivolumab
2.6.1.3	Study Treatment Administration for Ipilimumab
2.6.2	Adverse Events
2.6.3	Dose-Limiting Toxicities
2.6.4	Serious Adverse Events
2.6.6	Fatal Adverse Events
2.6.8	Adverse Events Leading to Discontinuation of INCAGN01876
2.6.9	Investigator-Identified Immune-Related Adverse Events
2.6.10	Sponsor-Identified Immune-Related Adverse Events
2.6.11	Infusion Reactions
2.7 Laboratory Data	
2.7.1	Clinical Laboratory Values - Hematology
2.7.2	Clinical Laboratory Values - Chemistry
2.7.3	Abnormal Clinical Laboratory Values
2.8 Vital Signs	
2.8.1	Vital Signs
2.8.2	Abnormal Vital Sign Values
2.8.3	Alert Vital Sign Values
2.9 ECG	
2.9.1	12-Lead Local ECG Values
2.9.2	Abnormal 12-Lead Local ECG Values
2.9.3	Alert 12-Lead Local ECG Values
2.10 Physical Examination	
2.10.1	Body Weight

## APPENDIX B. TECHNICAL REPORT FOR INTEGRATED BAYESIAN FUTILITY ANALYSIS

### Introduction

In this document, we present a strategy for pooling information across the tumor types and sequencing strategies defined in Section 3. The strategy is based on Simon et al (2016). The Bayesian pooling strategy will be used to carry out interim futility analyses and end-of-study efficacy analyses for each cohort. We begin with an introduction to the overall study design, and then we present simulation results and operating characteristics that illustrate the application of the Simon et al (2016) method in Part 2 of this study.

Phase 2 of the study will evaluate the efficacy of the recommended dose of INCAGN01876 as part of a doublet combination with the approved immunotherapy nivolumab and as part of a triplet combination with the approved immunotherapies nivolumab and ipilimumab. Subjects with endometrial, gastric, and SCCHN tumors will be evaluated in each of the doublet and triplet combinations. In addition, each of the doublet and triplet combinations will be tested using 3 dose-sequencing strategies: concurrent dosing of INCAGN01876 and immunotherapy, INCAGN01876 run-in Q2W for 2 doses followed by immunotherapy, and INCAGN01876 run-in Q2W for 2 doses followed by concurrent dosing of INCAGN01876 and immunotherapy.

In total, the study design for Phase 2 will test 18 unique tumor type (within doublet or triplet) and sequencing strategy cohorts. Each of the 18 cohorts will be evaluated by Simon 2-Stage design (Simon 1989). All sequencing strategies for a particular tumor type and doublet or triplet combination will use the same Simon 2-Stage design.

Table 12 shows the dose sequencing strategy and tumor type-specific strategy for each of the 18 cohorts used for pooling in the integrated Bayesian analysis. It is believed that activity or the lack of activity within any of the tumor types in a particular sequencing strategy will provide information about the activity in other tumor types in that sequencing strategy. It is also believed that activity or the lack of activity in 1 of the sequences tested on a specific tumor type will provide information about the activity in the other sequences tested on the same tumor type.

For the analysis within sequencing strategies, there will be 6 strata within each sequencing strategy. For the analysis within tumor types, there will be 3 strata within each tumor type.

Parameters to be specified a priori include  $\lambda$ , the probability of homogeneity, which controls the amount of borrowing;  $\gamma$ , the probability of activity in any stratum; and a vector of probabilities of length  $k$  equal to the number of strata, specifying individual probabilities of success in each stratum when the strata are not homogeneous,  $\Pr[p = q]$ . Here, the  $p$  vector represents the probability of activity in each stratum, and  $q$  is the outcome vector for  $p$ , each entry of  $q$  is  $p_1$  or  $p_0$ , corresponding to the probabilities of activity or inactivity, respectively, in the individual strata. This leads to  $2^k$  possibilities for the  $\Pr[p = q]$  vector. The individual  $p_1$  vectors are the target response rates from the Simon 2-Stage design for the given tumor types, and the individual  $p_0$  vectors are the unacceptable response rates from the same Simon 2-Stage designs. To clarify, the  $\Pr[p = q]$  vector is used in the calculation of the likelihood, but not in the calculation of the prior PoS.

To calculate prior PoS in any given cohort, we first determine all  $2^k$  permutations of successes and failures among the  $k$  cohorts and store these permutations in a matrix,  $m$ . Below is an example of the  $8 \times 3$   $m$  matrix for 3 strata. The rows of the  $m$  matrix represent the permutations, the columns represent the cohorts, and each entry in a row of 1 or 0 represents success or failure, respectively, for that cohort in the corresponding permutation.

$$m = \begin{bmatrix} 0 & 0 & 0 \\ 1 & 0 & 0 \\ 0 & 1 & 0 \\ 1 & 1 & 0 \\ 0 & 0 & 1 \\ 1 & 0 & 1 \\ 0 & 1 & 1 \\ 1 & 1 & 1 \end{bmatrix}$$

For rows 2 through  $2^k-1$  of the permutation matrix, where  $i$  represents the  $i$ th row and  $j$  represents the  $j$ th column, the prior PoS is defined as follows:

$$\text{PoS} = (1 - \lambda) \times \gamma^{\sum_{i=1}^{2^k} m_{ij}} (1 - \gamma)^{\sum_{i=1}^{2^k} 1 - m_{ij}},$$

where  $1 - \lambda$  is the probability that the cohorts are independent;  $\gamma$  is the probability of activity;  $\sum_{i=1}^{2^k} m_{ij}$  is the sum of the number of active cohorts under all permutations;  $1 - \gamma$  is the probability of inactivity; and  $\sum_{i=1}^{2^k} 1 - m_{ij}$  is the sum of the number of inactive cohorts under all permutations.

For row 1, which represents the case in which all cohorts are inactive, we add in the probability that the cohorts are correlated times the probability of inactivity:

$$\text{PoS} = (1 - \lambda) \times \gamma^{\sum_{i=1}^{2^k} m_{ij}} (1 - \gamma)^{\sum_{i=1}^{2^k} 1 - m_{ij}} + \lambda(1 - \gamma).$$

For row  $2^k$ , which represents the case in which all cohorts are active, we add in the probability that the cohorts are correlated times the probability of activity:

$$\text{PoS} = (1 - \lambda) \times \gamma^{\sum_{i=1}^{2^k} m_{ij}} (1 - \gamma)^{\sum_{i=1}^{2^k} 1 - m_{ij}} + \lambda\gamma.$$

Posterior PoS calculations based on sharing within the tumor types and within the sequencing strategies will be updated each time a subject with the tumor type of interest enrolls in the study using data already collected from subjects already on the study.

The posterior probabilities depend on the number of responses and sample sizes in each of the strata at the time, denoted by the vectors  $\mathbf{r}$  and  $\mathbf{n}$  respectively. The posterior PoS in tumor type  $i$  and sequence strategy  $j$  is proportional to the prior probability times the likelihood of the response data observed up to that point if the response numbers are given by the  $\mathbf{r}$  vector, if the sample sizes are given by the  $\mathbf{n}$  vector, and if  $q_{ij}$  is  $p_1$  times the same likelihood of the response data observed up to that point  $q_{ij}$  is  $p_0$ :

$$\begin{aligned}
 PoS &= \Pr(\mathbf{p} = \mathbf{q} | \lambda, \gamma, \mathbf{r}, \mathbf{n}) \\
 &= \left( (1 - \lambda) \times \gamma^{\sum_{i=1}^k m_{ij}} (1 - \gamma)^{\sum_{i=1}^k 1 - m_{ij}} \right) \\
 &\quad \times \prod_i \prod_{j, q_{ij}=p_1} q_{ij}^{r_{ij}} (1 - q_{ij})^{n_{ij} - r_{ij}} \times \prod_i \prod_{j, q_{ij}=p_0} q_{ij}^{r_{ij}} (1 - q_{ij})^{n_{ij} - r_{ij}}
 \end{aligned}$$

As an example of the PoS calculation, we look at a simplified example with 3 strata in [Table B1](#). Suppose that we observe the following results for the evaluable subjects in a study with 3 separate Simon 2-Stage designs with target rates of 0.25 and unacceptable rates of 0.05. The optimal Simon 2-Stage design with these criteria has an interim sample size of 19, total sample size of 55,  $r = 3, r = 12$ . The PoS calculation for each controls the degree of sharing of data between the strata and  $\gamma$  as the prior probability of activity for a given cohort. Note that the parameter  $\lambda$  has a direct relationship with the calculated PoS value across the 3 stratum.

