**Table B1: Example PoS Calculations for 3 Stratum**

Stratum	1	2	3
Responders/evaluable subjects	6/20	3/10	1/5
PoS based on $\lambda = 0.5$ and $\gamma = 0.33$	0.99	0.98	0.90
PoS based on $\lambda = 0.05$ and $\gamma = 0.33$	0.99	0.93	0.18

For the purposes of this analysis, we will specify a single value for  $\lambda$  and  $\gamma$ , so that the rate of sharing within sequences and tumor types will be equal, and the prior PoS assumed within strata in the pooling strategies will be equal. The PoS in tumor type (tumor type  $i$  and sequencing strategy  $j$ ) will be denoted by  $PoS1_{ij}$ , and the PoS within sequencing strategy (tumor type  $i$  and sequencing strategy  $j$ ) will be denoted by  $PoS2_{ij}$ .

Based on the results of the 2 calculated posterior PoS values, a tumor-sequence pair ( $i, j$ ) will be considered open for randomization if either  $PoS1_{ij}$  or  $PoS2_{ij}$  is greater than 20%. Otherwise, the tumor-sequence pair will be suspended with the possibility of being re-opened after more data have accrued and subsequent posterior PoS values are greater than 20% for the tumor-sequence pair.

At the end of the study, overall PoS tests will be performed using both  $PoS1_{ij}$  and  $PoS2_{ij}$ . A tumor-sequence strategy will be considered successful at the end of the study if either  $PoS1_{ij}$  or  $PoS2_{ij} > 80\%$ .

Each time a subject with the tumor type of interest is enrolled, 2 PoS calculations will be performed using the evaluable subjects: the PoS in tumor type (tumor type  $i$  and sequencing strategy  $j$ ),  $PoS1_{ij}$ , and PoS within sequencing strategy (tumor type  $i$  and sequencing strategy  $j$ ),  $PoS2_{ij}$ .

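### The probability-of-success formulas printed in SAP Appendix B are wrong as written: the posterior omits the λ terms, the prior sums over the wrong index, and one Table B1 cell should be 0.58, not 0.18

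*SAP*

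**What the plan says.** SAP section 9.1.2.2 closes a Phase 2 cohort when both of its PoS values fall below 20%, sets λ = γ = 0.4, and refers to Appendix B and a cited basket-design paper for the method. Protocol sections 7.2 and 9.6.2 run this rule inside the IRT and call a cohort successful at study end if either PoS exceeds 80%.

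Appendix B builds the calculation in three steps.

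- **Prior.** Each row of the matrix m is one pattern of active and inactive cohorts. The exponent of γ is displayed as a sum over i = 1 to 2^k, and the text says it "is the sum of the number of active cohorts under all permutations". For the all-inactive row "we add in the probability that the cohorts are correlated times the probability of inactivity"; for the all-active row "we add in the probability that the cohorts are correlated times the probability of activity".
- **Posterior.** It "is proportional to the prior probability times the likelihood of the response data observed up to that point". The display beneath has (1−λ) times powers of γ and 1−γ, times the likelihood. It has no λγ or λ(1−γ) term, no normalising sum, and no sum over rows to give one cohort's PoS.
- **Example.** Table B1, "Example PoS Calculations for 3 Stratum", uses "target rates of 0.25 and unacceptable rates of 0.05" and γ = 0.33. The text adds that λ "has a direct relationship with the calculated PoS value across the 3 stratum".

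**The concern.** λ is the only parameter that lets cohorts inform one another, and it enters only through the two terms missing from the posterior display. A constant (1−λ) on every row disappears on normalising. A programmer who follows the display therefore gets independent cohorts; one who follows the printed prior exponents gets a different wrong answer. The worked example cannot settle which reading is right, because one of its cells fits none of them.

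At stake is a rule that closes cohorts at 20% and declares success at 80%, with the operating characteristics quoted in SAP Table 13 and Table B3.

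**Working it through.** **Inputs.** Table B1: 6/20, 3/10 and 1/5 responders; p0 = 0.05, p1 = 0.25; γ = 0.33; λ = 0.5 and 0.05. Stated PoS: 0.99 / 0.98 / 0.90 (λ = 0.5) and 0.99 / 0.93 / 0.18 (λ = 0.05). Trial values: λ = γ = 0.4, with the designs in SAP Table 2.

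**1. Likelihood ratios.** LR = (p1/p0)^r × ((1−p1)/(1−p0))^(n−r).

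- 6/20: 5^6 × (0.75/0.95)^14 = 570.9
- 3/10: 5^3 × (0.75/0.95)^7 = 23.89
- 1/5: 5 × (0.75/0.95)^4 = 1.942

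**2. Intended formula.** Sum over all rows with row-wise exponents and the λ terms on the first and last rows, then normalise. Write ind_j = γLR_j/(γLR_j + 1−γ) and A = (1−λ) × Π(γLR + 1−γ). Then

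PoS_j = [A × ind_j + λγΠLR] / [A + λ(1−γ) + λγΠLR].

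Here Π(γLR + 1−γ) = 189.06 × 8.555 × 1.311 = 2,120 and ΠLR = 26,494. For stratum 3, ind = 0.33 × 1.942/(0.33 × 1.942 + 0.67) = 0.489.

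- λ = 0.5: (1,060 × 0.489 + 4,371)/(1,060 + 0.335 + 4,371) = 0.900, as stated.
- λ = 0.05: (2,014 × 0.489 + 437)/(2,014 + 0.034 + 437) = 0.580, against the stated 0.18.

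**3. All cells, by exact enumeration of the eight rows.**

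| Version | λ = 0.5 | λ = 0.05 |
|---|---|---|
| Stated in Table B1 | 0.99 / 0.98 / 0.90 | 0.99 / 0.93 / 0.18 |
| Intended formula | 0.999 / 0.985 / 0.900 | 0.997 / 0.936 / 0.580 |
| Posterior as displayed | 0.996 / 0.922 / 0.489 | 0.996 / 0.922 / 0.489 |
| Prior with exponents as printed | 1.000 / 0.999 / 0.996 | 1.000 / 0.993 / 0.939 |

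The intended formula matches five of six cells when truncated to two decimals. Using 0/5 in stratum 3 gives 0.179 at λ = 0.05, but 0.587 instead of 0.90 at λ = 0.5, so changed data do not explain both rows.

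**4. Printed prior.** Every column of m sums to 2^(k−1), so every row receives the same (1−λ) part, (1−λ) × [γ(1−γ)]^(2^(k−1)). The first and last rows still add their λ terms, which together equal λ. At λ = γ = 0.4 and k = 3 the total is 8 × 0.6 × 0.24^4 + 0.4 = 0.416. At k = 6 it is 0.400. Neither is 1. Almost all the weight sits on the all-inactive and all-active rows, so this version over-borrows.

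**5. Error rate with the posterior as displayed.** Each cohort then stands alone, so both poolings give the same PoS. At full enrollment PoS > 80% needs at least 17/51, 13/46, 22/48 or 20/50 responders. Combined with the Simon Stage 1 rule, the per-cohort null rejection rates are:

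- endometrial doublet 0.0142; SCCHN and gastric doublets 0.0121 each
- endometrial triplet 0.0136; SCCHN and gastric triplets 0.0122 each

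These sum to 0.0765. Over three sequences the expected number of false positives is 3 × 0.0765 = 0.229, and the probability of at least one is 1 − Π(1 − rate)^3 = 0.206. SAP Table 13 states 0.104 and 0.0876. As a check on inputs, the 18 separate Simon designs give an expected sample size of 457.2, as stated.

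**6. Simulation of the 18 cohorts** (Table B2 accrual, 16-week delay, 2,500 global-null replicates; pausing at n1 and re-opening varied because they are not fully specified).

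| Version | P(≥ 1 false positive) | Expected false positives |
|---|---|---|
| SAP Table 13 | 0.0876 | 0.104 |
| Intended formula | 0.086–0.108 | 0.094–0.121 |
| Posterior as displayed | 0.17–0.21 | 0.19–0.24 |
| Prior as printed | 0.014–0.038 | 0.035–0.111 |

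The printed-prior version looks safe under the global null. With one tumor type or one sequence truly active, its false-positive probability is about 0.8 (0.807 and 0.783), where Table B3 states 0.135 and 0.150.

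**7. Effect on one decision.** Take SCCHN doublet data of 6/16 in Group F and 0/4 in Group H, with p0 = 0.15 and p1 = 0.35. For H alone, LR = (0.65/0.85)^4 = 0.342 and PoS = 0.4 × 0.342/(0.4 × 0.342 + 0.6) = 0.19, so H closes. With borrowing from F the tumor-type PoS is 0.33, so H stays open.

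**The case against.** The strongest reply is that the method is recoverable. The sentence above the display says prior times likelihood, the λ terms are stated just before it, the text says λ controls borrowing, and SAP section 9.1.2.2 also cites the source paper. This stands in part: an informed statistician would reach the intended formula, and Appendix B is not the only pointer to the method. It does not rescue the display, nor the prior exponents, where words and symbols agree on the wrong index.

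A reader might go further and infer any of the following. The documents do not support them.

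- *The sponsor's simulations are wrong.* Five Table B1 cells and the stated 0.0876 agree with the intended formula, so the simulation code probably includes the λ terms.
- *Both misprints remove borrowing.* Only the displayed posterior does. The printed prior keeps its λ terms on the first and last rows, so it is not uniform, and it over-borrows.
- *Table B1 fails altogether, or would let a wrong program pass.* One cell is off, and neither misprinted version reproduces the table. It is also described as a simplified example, not a validation case, so its 0.18 closes no cohort.

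The SCCHN illustration in the working is close to the cutoff: with 0/3 in H the displayed formula gives 0.23 and H stays open either way. Finally, Protocol Amendment 5 says enrollment is complete, so the futility rule can close nothing further. The 80% test at study end still depends on the formula.

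**Conclusion.** The point holds as a defect in the printed specification. The displayed posterior and the printed prior are each wrong as written, in opposite directions, and neither reproduces Table B1 or the stated operating characteristics. For the displayed posterior the global-null false-positive probability is 0.206 against 0.0876, a little over twice as high.

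The Table B1 values, the 0.206 and the 0.229 are exact. The last two assume full enrollment of every cohort that passes Stage 1, with no PoS stopping along the way. The simulated ranges depend on accrual, pausing and re-opening details that the SAP leaves open; their Monte Carlo standard error is about 0.006 to 0.008. The sponsor's R code and the IRT program are not in the documents, so nothing shows that a wrong formula was run.

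A minor slip sits beside this. The example design 3/19, 12/55 is called optimal for 0.05 versus 0.25, where its power is only 0.55. It fits 0.15 versus 0.30 (Type I error 0.048, power 0.80). It enters no PoS calculation.

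**What to change.** Amend SAP Appendix B as follows.

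- Write the prior for row i with exponents summed over cohorts j = 1 to k: (1−λ) × γ^(Σ_j m_ij) × (1−γ)^(k − Σ_j m_ij), plus λ(1−γ) for the all-inactive row and λγ for the all-active row.
- Use that full prior in the posterior display.
- State that a cohort's PoS is the sum of prior times likelihood over the rows where it is active, divided by the sum over all rows.
- In Table B1, change 0.18 to 0.58.
- Correct the response rates given for the example design, or replace the design.

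Then check the IRT program and the end-of-study PoS program once against the corrected formula, using the corrected Table B1 as a test case. The cost is a short text correction and one program check. No design parameter changes. The simulations need re-running only if that check shows their code differs from the intended formula.

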**Table B1: Example PoS Calculations for 3 Stratum**

Stratum	1	2	3
Responders/evaluable subjects	6/20	3/10	1/5
PoS based on $\lambda = 0.5$ and $\gamma = 0.33$	0.99	0.98	0.90
PoS based on $\lambda = 0.05$ and $\gamma = 0.33$	0.99	0.93	0.18

For the purposes of this analysis, we will specify a single value for  $\lambda$  and  $\gamma$ , so that the rate of sharing within sequences and tumor types will be equal, and the prior PoS assumed within strata in the pooling strategies will be equal. The PoS in tumor type (tumor type  $i$  and sequencing strategy  $j$ ) will be denoted by  $PoS1_{ij}$ , and the PoS within sequencing strategy (tumor type  $i$  and sequencing strategy  $j$ ) will be denoted by  $PoS2_{ij}$ .

Based on the results of the 2 calculated posterior PoS values, a tumor-sequence pair ( $i, j$ ) will be considered open for randomization if either  $PoS1_{ij}$  or  $PoS2_{ij}$  is greater than 20%. Otherwise, the tumor-sequence pair will be suspended with the possibility of being re-opened after more data have accrued and subsequent posterior PoS values are greater than 20% for the tumor-sequence pair.

At the end of the study, overall PoS tests will be performed using both  $PoS1_{ij}$  and  $PoS2_{ij}$ . A tumor-sequence strategy will be considered successful at the end of the study if either  $PoS1_{ij}$  or  $PoS2_{ij} > 80\%$ .

Each time a subject with the tumor type of interest is enrolled, 2 PoS calculations will be performed using the evaluable subjects: the PoS in tumor type (tumor type  $i$  and sequencing strategy  $j$ ),  $PoS1_{ij}$ , and PoS within sequencing strategy (tumor type  $i$  and sequencing strategy  $j$ ),  $PoS2_{ij}$ .

### Simulations and Operating Characteristics

Computer simulations were conducted in R to compare the operating characteristics of the Bayesian basket trial design with the operating characteristics of 18 separate Simon 2-Stage designs. We investigated 6 scenarios that would represent different configurations of null and alternative hypotheses (corresponding to inactivity of drug and activity of drug) within the sequencing strategies and tumor types. For the global null hypothesis of no activity in any cohort (Scenario 1), 2500 replications were performed. All other scenario results were simulated using 1000 replications.

In the computer simulations, we assumed the prior probability of correlation between cohorts within tumor types and sequencing strategies to be  $\lambda = 0.4$  and prior probability of activity to be  $\gamma = 0.4$ .

The Simon 2-Stage designs used in the simulations are given in [Table 2](#). The  $p_1$  and  $p_0$  values are assumed not to change with sequencing strategy. For example, for each of the 3 sequencing strategies tested on the SCCHN doublet,  $p_1 = 0.35$  and  $p_0 = 0.15$ . The total sample sizes if each cohort reached full enrollment are given by the  $n$  column in [Table 2](#).

Within the simulations, a tumor-sequence pair  $(i, j)$  was stopped if neither  $PoS1_{ij}$  nor  $PoS2_{ij}$  was  $\geq 20\%$  at any point. In addition, the first stage rule for the Simon 2-stage design was also applied where enrollment was halted unless more than  $r_1$  of the first  $n_1$  subjects responded to treatment within a tumor-sequence pair. The method rejected the null hypothesis of no activity in a cohort at the end of the study if either  $PoS1_{ij}$  or  $PoS2_{ij} > 80\%$ .

For purposes of the simulation, tumor responses were programmed to occur 16 weeks after start of treatment. A 7-month period was assumed between the opening of the doublet and triplet tumor type cohorts. During the first 7 months, subjects were equally distributed among endometrial, gastric, and SCCHN tumor types and subjects of each tumor type were randomly assigned to the 3 sequence strategies. After the first 7 months, the triplet tumor type cohorts opened, subjects were still equally distributed among endometrial, gastric, and SCCHN tumor types and were sequentially assigned to the doublet and triplet sequencing strategy-specific treatment groups that were available after the interim futility and Simon 2-Stage futility rules were applied. Enrollment in each tumor type was assumed to occur over a 33-month period with subjects equally distributed between the 3 tumor types over that period and rates of enrollment increasing over the length of enrollment. Enrollment was generated by an exponential(0.7) curve. Projected maximum enrollment by quarter is defined in [Table B2](#).

